#### Statistical Analysis Plan

Data will be analyzed using SPSS Statistics 26.0 for Mac. We will use Pearson's chi-squared ( $\chi 2$ ) and one-way analysis of variance (ANOVA) to compare demographic variables and baseline psychopathological characteristics of the three groups. To represent within-participant dependencies in the models, we will specify an unstructured correlation matrix. We will first apply a full factorial model across the four time points (baseline, post-intervention, 14- and 30-day follow-ups) for treatment-seeking intentions and three time points (baseline, 14- and 30-day follow-ups) for clinical symptoms. Group × time interaction terms will test the intervention effect hypothesis of greater treatment-seeking in the two video groups. If between-group differences are found, post hoc tests will be used to compare each group pair, including the overall changes from baseline assessment to 30-day follow-up. Effect sizes will be reported using Cohen's d when appropriate. All statistical tests will be two-sided, using  $\alpha < 0.05$ .

Protocol Title: Version Date: The COVID-19 and healthcare workers: an 10/20/2020

active intervention

Protocol Number:

8032

Clinic: First Approval:

07/13/2020 **Anxiety Disorders Clinic** 

**Expiration Date:** No Expiration

Contact Principal Investigator: Principal Investigator: [name], PHD

**[name]** Email:

[contact]

Co-Investigator(s): [contact] [name], MPH

> Research Chief: [name]

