Many health care providers reluctant to seek support from friends and family, as well as mental health care due to stigma and fear. Despite enduring symptoms, they may wait months to years before they seek help. Applying strategies to reduce stigma and fear towards mental health care and improve help seeking behavior may ameliorate impaired functioning and reduce risks for long-term psychiatric illness. Studies have shown that social contact is the most effective type of intervention to reduce stigma-related attitudes and to improve help-seeking behavior. The overarching goal of this study is to examine the efficacy of video intervention in reducing stigma and fear, and improving help seeking behavior among health care providers (N=1,200), with pre-, post- and follow up assessments (day 14, day 30 and day 90). Participants will be randomly assigned to either a) a video-based intervention (day 1 and a "booster intervention" of the same content on day 14 of the study) featuring the personal story of a health care provider with COVID-19, his struggles and barriers to care, (b) video-based intervention (day 1 only), and a written description of the same story on day 14 (c) no-intervention control arm (questionnaires only). We aim to (1) determine whether video-based intervention reduce stigma and fear, and increase helpseeking behavior in relation to COVID-19 among health care providers, and (2) compare high risk areas (e.g., NY) to low risk areas (e.g., Montana) on intervention outcomes, and (3) test whether symptoms of depression, anxiety, PTSD and Moral Injury, that will be measured by Patient Health Questionnaire (PHQ-9), Generalized Anxiety Disorder (GAD-7), the Primary Care PTSD Screen for DSM-5 (PC-PTSD-5), and the Moral Injury Events Scale (MIES) would change overtime.

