## **Specific Aims and Hypotheses**

Specific Aims and Hypotheses

The overarching goal of this study is to examine the effect of video intervention in reducing stigma and fear, and improving help seeking behavior among health care providers across the US.

In a sizable randomized controlled trial (N=1,200, general population), with pre-, post- and follow-up assessments (day 14, day 30 **and 90 day**), we aim to (1) determine whether video-based intervention reduce stigma and fear, and increase help-seeking behavior in relation to COVID-19 among health care providers, and (2) compare high risk areas (e.g., NY) to low risk areas (e.g., Montana) on intervention outcomes, and (3) test whether symptoms of depression, anxiety, PTSD and Moral Injury, that will be measured by Patient Health Questionnaire (PHQ-9), Generalized Anxiety Disorder (GAD-7), the Primary Care PTSD Screen for DSM-5 (PC-PTSD-5), and the Moral Injury Events Scale (MIES) would change overtime.

Hypotheses: We hypothesize that (1) the brief video intervention will have greater impact in reducing stigma and fear, and in increasing help-seeking behavior in relate to COVID-19 than the control groups in comparison to pre-intervention and to non-video conditions, (2) High risk areas will have increased baseline rates of anxiety, depression and PTSD, and (3) the brief video is expected to have greater impact in reducing symptoms of depression, GAD and PTSD.

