#### **Assessment Instruments**

Create a table or give a brief description of the instruments that will be used for assessment Questions for the pre- and post-intervention (day 1) and follow-ups (day 14, day 30 and **day 90**). Baseline Questionnaire (will be conducted pre intervention only) will include four questions regarding demographics (age, sex, ethnicity and race). Based on previous studies it is estimated the response time will be around 30 seconds.

Three questionnaires will be conducted at pre- and post-intervention (day 1) and follow-up (day 14, day 30 and day 90):

- 1. Attitude towards COVID-19 attitude towards COVID-19 questions were adapted from a measure created by Berger et al. about stigma and fear towards people with HIV. The questionnaire will include six questions and based on previous studies it is estimated the response time for 50 seconds.
- 2. Attitude towards seeking help Attitude towards help seeking will be based on the ATSPPH-SF (Attitudes Towards Seeking Professional Psychological Help Scale), and will include 5 questions (0-disagree, 3-agree). One table will be created to include all 5 questions in one screen. Based on previous studies it is estimated the response time will be around 40 seconds.
- 3. COVID-19 related behaviors and experiences was developed by the researchers and will include six questions regarding social media use, news consumption, social contact, previous contact with a known COVID-19 patient and if the participant has been tested for COVID-19. It is estimated the response time will be around 50 seconds.

Three questionnaires will assess clinical symptoms and will be conducted at pre-intervention (day 1) and follow-up (day 14, day 30, and **day 90**):

- 1. GAD-7 questionnaire will include 7 questions that assess anxiety
- 2. PHQ-9 questionnaire will include 9 questions to assess depression
- 3. Primary Care PTSD screen for DSM-5 will include 5 yes/no questions to assess PTSD. Three tables will be created, one for each questionnaire. Based on previous studies it is estimated the response time will be 150 seconds.

One questionnaire will assess Moral Injury (MIES), and includes 9 items (50 seconds).

In sum, the estimate time for day 1 (pre and post intervention) is 7-9 minutes for intervention groups and 5-7 minutes for control. The estimate time for each follow up is 4-7 minutes (days 14, 30 and 90).

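### The SAP plans no analysis of stigma and fear, the first effect in Aim 1 and Hypothesis 1, and stops at day 30 although the protocol runs to day 90

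*Combined protocol and SAP*

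**What the plan says.** The SAP has two modelled outcome domains. For the first it says: "We will first apply a full factorial model across the four time points (baseline, post-intervention, 14- and 30-day follow-ups) for treatment-seeking intentions". The second is clinical symptoms, at baseline, day 14 and day 30. The group × time terms are tied to greater treatment-seeking in the two video groups, and the post hoc comparisons run from baseline to day 30.

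The protocol asks for more.

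- **Aims.** Specific Aims and Hypotheses sets Aim 1 as to "determine whether video-based intervention reduce stigma and fear, and increase help-seeking behavior in relation to COVID-19 among health care providers". Hypothesis 1 is that "the brief video intervention will have greater impact in reducing stigma and fear, and in increasing help-seeking behavior". Stigma and fear come first in both.
- **Stigma/fear instrument.** Assessment Instruments describes a COVID-19 attitude scale adapted from a measure "about stigma and fear towards people with HIV. The questionnaire will include six questions".
- **Schedule.** For that scale, the five-item help-seeking attitude scale and a questionnaire on COVID-19 behaviours: "Three questionnaires will be conducted at pre- and post-intervention (day 1) and follow-up (day 14, day 30 and day 90"). For symptoms: "Three questionnaires will assess clinical symptoms and will be conducted at pre-intervention (day 1) and follow-up" at days 14, 30 and 90.
- **Day 90.** The Amendment section adds this wave to learn about longer-term effects and whether changed intentions turn into changed behaviour. A new multiple-answer item at day 90 asks about medication started, psychological treatment started, professionals contacted, and plans to contact them.

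**The concern.** An analyst who follows the SAP exactly would produce no test of the first-named effect in Hypothesis 1, no estimate at day 90, and no answer to the question for which the amendment was written. Those results could still be reported, but the score, the model and the contrast could then be chosen after the data are seen.

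The room for choice is real. The six-item scale has no stated response options, total score or direction. The day-90 item lets a participant tick several answers, and nothing says which of them count as help-seeking.

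There is also a question of construct. The scale derives from stigma towards people with an infection, whereas the Lay Summary speaks of stigma towards care: "Applying strategies to reduce stigma and fear towards mental health care and improve help seeking behavior may ameliorate impaired functioning". The Background section uses the same idea. The documents never say which instrument carries the stigma and fear of Aim 1.

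**Working it through.** **1. Coverage.** The SAP's own figures are four time points for treatment-seeking intentions and three for symptoms. Set against Assessment Instruments and the day-90 item:

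| Outcome | Assessments scheduled | Assessments in a planned analysis |
|---|---|---|
| Six-item COVID-19 attitude scale | 5 (pre, post, days 14, 30, 90) | 0 |
| Help-seeking attitude scale, taken to be the SAP's treatment-seeking intentions | 5 | 4 |
| Symptom questionnaires (GAD-7, PHQ-9, PC-PTSD-5) | 4 (pre, days 14, 30, 90) | 3 |
| Day-90 help-seeking item | 1 | 0 |

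Moral injury is left out of the count because the protocol gives that questionnaire no assessment times.

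**2. Could the attitude scale sit inside a modelled outcome?** Not under clinical symptoms: the protocol lists the symptom questionnaires separately, and the SAP's symptom model has no post-intervention time point, while this scale has one. Not under treatment-seeking intentions: help-seeking attitude is a separate five-item instrument.

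**3. Does the amendment explain the gaps?** It added day 90, one item and a change in payment. A SAP written before it would lack day 90. It did not add stigma and fear as an aim, so it does not explain that omission.

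**4. Can the planned model test the day-90 item?** Group × time df = (groups − 1)(time points − 1). With three groups and one time point this is 2 × 0 = 0. No earlier instrument listed asks about treatment or contact with a professional, so there is no baseline value. The arms can still be compared directly because they are randomised, but the SAP names no method for that.

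**5. What would adding day 90 to the existing omnibus tests cost?** By the same formula:

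- help-seeking, 4 to 5 time points: 2 × 3 = 6 df becomes 2 × 4 = 8 df;
- symptoms, 3 to 4 time points: 2 × 2 = 4 df becomes 2 × 3 = 6 df.

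For 80% power at two-sided 0.05, the chi-square noncentrality is 13.62 on 6 df and 11.94 on 4 df. If day 90 adds nothing to the effect, noncentrality stays the same while df rise: 13.62 on 8 df gives power 0.751, and 11.94 on 6 df gives 0.735. The loss is from 80% to about 74–75%. A separate day-90 contrast avoids it.

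**6. Error rate.** The SAP tests everything at 0.05 with no rule across outcomes. Two independent outcomes give 1 − 0.95² = 0.0975. Independence is an assumption; positively correlated outcomes would give less.

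**The case against.** The strongest reply has three parts.

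*The mapping is not settled.* If Aim 1 means stigma towards mental health care, the nearest listed instrument is the help-seeking attitude scale, which the SAP appears to model. This stands as a caution. A reader might infer that the six-item scale simply is the Aim 1 measure; the documents do not say so. The reference to COVID-19 in Aim 1 and the scale's origin in a stigma and fear measure favour that reading without proving it. Equally, treating treatment-seeking intentions as the help-seeking attitude scale is an inference. Neither doubt removes the gap: under either reading the SAP does not say how stigma and fear are to be tested.

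*The SAP may have chosen one hypothesis on purpose.* No document labels stigma as primary, and the hypothesis, instruments and assessment times are all specified in advance. That is true, and it limits the point to the missing analysis. It does not supply one for an effect that Hypothesis 1 states.

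*Detail may lie elsewhere.* The SAP text carries no date of its own, and copies of the non-standard instruments are not in the public file. Scoring may be documented there, so the statement that no score or direction is given applies only to the public text. The Amendment section also narrows the day-90 item towards contact with professionals, so its scoring is less open than the six answers suggest. It is still not defined as an endpoint.

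**Conclusion.** The point holds and should be corrected before results are seen. Planned coverage is 0 of 5 assessments for the apparent stigma/fear measure, 4 of 5 for help-seeking attitude, 3 of 4 for symptoms and 0 of 1 for the day-90 behaviour item. The weight rests on stigma and fear; the day-90 gaps may be no more than a SAP left behind by the amendment.

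Three stronger readings are not supported.

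- *That the planned analyses are invalid.* The day-30 tests of help-seeking and symptoms are unaffected.
- *That the missing stigma test would be informative.* Assuming equal allocation, 1,200 gives 400 per arm, and a single pairwise contrast has 80% power at 2.802 × √(2/400) = 0.198 SD of the change score. But the SAP tests group × time first. If one arm differs from the other two by 0.198 SD in one contrast only, noncentrality is 400 × 0.198² × 2/3 = 10.45, which gives about 61% power on 8 df (five time points) or 67% on 6 df (four). The documents state no important difference, standard deviation or dropout rate, so no claim about informativeness can be made.
- *That open scoring of the day-90 item inflates the false-positive rate by a known amount.* The documents give no expected frequency for any answer, so the inflation cannot be sized from them.

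**What to change.** Amend the SAP before any between-arm results are seen.

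1. **Stigma and fear.** State which instrument measures it, and confirm that the help-seeking attitude scale is what the SAP calls treatment-seeking intentions. Give the six-item scale's total score and direction, and analyse it as a named outcome in the same group × time model.
2. **Day 90.** Keep the day-30 models as planned. Add the baseline-to-day-90 change as a separate named contrast for stigma/fear, help-seeking and symptoms.
3. **Day-90 behaviour.** Define one binary endpoint that matches the amendment's purpose, for example treatment started or professionals contacted (answer 2 or 3). Use any of answers 1–3 as a sensitivity analysis, count answer 4 as an intention, and treat a refusal to answer as missing. Compare arms by logistic regression and report pairwise risk differences with 95% confidence intervals.
4. **Hierarchy.** State which outcome is primary and label the others secondary. The choice belongs to the investigators.

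The cost is SAP wording, two extra models and the day-90 contrasts, with more tests to interpret. All the data are already scheduled.

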# **Description of Subject Population**

#### Sample #1

Specify subject population

US adults health care workers

Number of completers required to accomplish study aims

1200

Projected number of subjects who will be enrolled to obtain required number of completers

1200

Age range of subject population

18-80

Gender, Racial and Ethnic Breakdown

It is expected the sample will roughly mirror the US healthcare workers population:

Anticipated gender distribution: 73% female, 27% male

Anticipated racial distribution: 72% white only, 21% African American only, 5% Asian only, 2% other, 5%

2+ races

Anticipated Hispanic Ethnic Distribution: 10% Hispanic, 90 % Non-Hispanic

Description of subject population

Participants recruited using Amazon Mechanical Turk (AMT) will be adults in the U.S.

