## **Study Procedures**

Describe the procedures required for this study

Participants will be randomly assigned to either a) a 120-second video-based intervention (day 1 and a "booster intervention" of the same content on day 14 of the study) featuring the personal story of a health care provider with COVID-19, his struggles and barriers to care, (b) video-based intervention (day 1 only), and a written description of the same story on day 14 (c) no-intervention control arm (questionnaires only).

Participants of all study arms will be invited to participate in a follow up survey in days 14, 30 and 90. We will invite the participants by using AMT messaging system.

The video content/written vignette: "Martha is a 35-year-old nurse who lives in NYC with her husband (Dave). She works at intensive care unit in a large hospital, and her husband was fired recently from his job as a waiter due to COVID-19. She has never been diagnosed with anxiety, depression or any other mental health issues. Lately, she finds herself experiencing nightmares as well as unexpected fears. She is feeling worried about money, about what might happen if she becomes infected with COVID-19, and about the safety of her parents as well. To Martha it seems that everything has changed since the pandemic began. Recently these worries mean she has had trouble falling asleep, she feels depressed and he feels anxious. Her husband suggested that she could try seeking help. When he first suggested this she dismissed him

saying, "What if people know I went to a psychologist? They might think I'm crazy. Also, what if they suggest I take meds? I don't want to take any... And if my colleges found out they might think I'm weak...". Martha was very resistant to even the idea at first. After a while however, when she realized that how she felt was only getting worse, she agreed to seek professional help. She found a therapist that she now meets with once a week, and since this started, she has reported that she is feeling much better."

You can upload charts or diagrams if any

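### The full factorial group-by-time model gives each randomised arm its own baseline mean, so its change-from-baseline tests are valid but less precise than a common-baseline model on the same data.

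*Combined protocol and SAP*

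**What the plan says.** The Statistical Analysis Plan section specifies, for treatment-seeking intentions, "a full factorial model across the four time points (baseline, post-intervention, 14- and 30-day follow-ups". For symptoms it uses "three time points (baseline, 14- and 30-day follow-ups) for clinical symptoms". Within-participant dependence is handled as follows: "we will specify an unstructured correlation matrix". The test of the hypothesis is that group-by-"time interaction terms will test the intervention effect hypothesis of greater treatment-seeking in the two video groups". If groups differ, "post hoc tests will be used to compare each group pair, including the overall changes from baseline assessment to 30-day follow-up".

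Baseline is otherwise used only to compare the groups' characteristics by chi-squared and ANOVA, which adjusts nothing. No section constrains the baseline means to be equal or enters baseline as a covariate.

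Two other sections bear on the point. Study Procedures states random allocation: "Participants will be randomly assigned to either a) a 120-second video-based intervention", with two further arms. Assessment Instruments places the scales before the intervention: "Three questionnaires will assess clinical symptoms and will be conducted at pre-intervention (day 1) and follow-up"; the help-seeking items are likewise given before and after it on day 1.

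**The concern.** A full factorial model has a free mean in every arm-by-time cell, including three separate baseline means. The interaction test and the baseline-to-day-30 comparisons are then differences in change scores, and chance baseline differences between arms enter with a coefficient of one. Under randomisation, with baseline measured before the arm is known, the three baseline means are equal in expectation. Estimating them separately discards that information.

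The interaction is the stated test of the intervention hypothesis, and the pairwise comparisons depend on it. A loss of power there carries through to everything after it. The point covers only the interaction and the change-from-baseline contrasts, because the plan does not specify the other post hoc comparisons.

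**Working it through.** **Inputs from the documents.** Three randomised arms; four time points for help-seeking and three for symptoms; two-sided 5% tests. The entry for "Number of completers required to accomplish study aims" is 1200, and projected enrolment is also 1200. The documents state no power calculation, so there is no figure of theirs to reproduce.

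**Assumptions.** Equal allocation (1200/3 = 400 per arm), since no ratio is given. Equal variances and one correlation ρ between all visits, unless stated. An effect of 0.15 SD in both video arms at every follow-up. In the loss scenario, none lost at the same-day post-intervention assessment, 20% by day 14 and 40% by day 30, equal across arms and at random.

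**Variance of a pairwise contrast, complete data, n per arm.** With baseline SD s0 and follow-up SD st:

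- Planned change contrast: (2/n)(s0² + st² − 2ρ·s0·st)
- Common-baseline contrast: (2/n)·st²(1 − ρ²)
- Planned minus common: (2/n)(s0 − ρ·st)², which is never negative and is zero only if ρ·st = s0

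With equal SDs the ratio, common over planned, is (1 − ρ²)/[2(1 − ρ)] = (1 + ρ)/2.

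**Example at ρ = 0.5, SD = 1, n = 400.** Planned: (2/400) × 2 × 0.5 = 0.00500, SE 0.0707. Common baseline: (2/400) × 0.75 = 0.00375, SE 0.0612. For 0.15 SD, 0.15/0.0707 = 2.12 gives 56% power and 0.15/0.0612 = 2.45 gives 69%.

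**Results.** Day-30 variances and joint tests come from generalised least squares information matrices for the three-arm design. Pairwise power uses the normal approximation; joint tests use the noncentral chi-squared distribution. Each arrow runs from the planned to the common-baseline model.

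| Quantity | ρ = 0.5 | ρ = 0.7 | ρ = 0.8 |
|---|---|---|---|
| Day-30 variance ratio, complete | 0.75 | 0.85 | 0.90 |
| Day-30 variance ratio, with loss | 0.83 | 0.90 | 0.93 |
| Day-30 pairwise power, complete | 56→69% | 78→84% | 92→94% |
| Day-30 pairwise power, with loss | 43→50% | 62→67% | 79→82% |
| Help-seeking interaction (6 df), complete | 59→83% | 84→93% | 96→99% |
| Help-seeking interaction (6 df), with loss | 55→76% | 80→90% | 95→97% |
| Symptom interaction (4 df), complete | 60→80% | 85→92% | 96→98% |
| Symptom interaction (4 df), with loss | 50→65% | 74→82% | 90→93% |

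At ρ = 0.9 the variance ratio is 0.95 complete and 0.97 with loss. The square roots of the with-loss ratios make day-30 intervals about 9%, 5%, 4% and 2% narrower at ρ = 0.5, 0.7, 0.8 and 0.9. With complete data, the common-baseline model matches the planned model's 1200 participants with 0.75 × 1200 = 900, 0.85 × 1200 = 1020 or 0.90 × 1200 = 1080.

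**Unequal SDs.** At ρ = 0.7 with complete data, the ratio is 0.63 if st/s0 = 0.8 and 0.97 if st/s0 = 1.2.

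**Declining correlations.** With baseline correlations of 0.9 (same day), 0.7 (day 14) and 0.6 (day 30), and follow-up correlations of 0.75 (post with day 14), 0.65 (post with day 30) and 0.75 (day 14 with day 30), the 6-df test gains almost nothing at 0.15 SD (99.5→99.8%). Day-30 pairwise power still rises from 66% to 76%, or from 52% to 58% with loss.

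**Validity.** In 4,000 simulated trials with complete data and an estimated covariance matrix, the 6-df type I error of the planned and baseline-adjusted tests (covariate form) was 5.1% and 4.9% at ρ = 0.5, 5.2% for both at 0.7, and 5.3% for both at 0.8. Simulated power was 58.7→82.3%, 84.6→93.8% and 96.9→98.9%, in line with the table.

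**The case against.** The strongest reply is that nothing here is wrong. A full factorial repeated-measures model with an unstructured matrix is a recognised way to test differences in change, and the plan asks for changes from baseline. This stands: the point concerns efficiency.

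The size is also wholly assumed. At larger effects the gain shrinks because power is already high: at 0.20 SD and ρ = 0.7 with complete data, the 6-df test goes from 98.6% to 99.8% and the day-30 comparison from 95.5% to 97.7%. This stands in part. At 0.20 SD and ρ = 0.5 with loss, the day-30 comparison still moves from 66% to 74%.

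A constant ρ is doubtful for help-seeking, because the same items are answered before and after a two-minute video in one session. Under declining correlations the interaction gain at 0.15 SD is negligible. That is largely a ceiling effect: at 0.10 SD the same pattern gives 80→85%, and the day-30 contrast gains at 0.15 SD too.

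Finally, with dropout a common-baseline analysis needs a missing-data assumption, and the plan does not say whether it uses likelihood or estimating equations. The planned model needs the same assumption, so this does not separate the two, but the SAP should state it. The protocol's day-90 visit is absent from the SAP's time points; that is a separate gap, and it changes only the degrees of freedom below.

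**Conclusion.** The concern holds. The planned interaction and change-from-baseline contrasts are unbiased with correct type I error, but they are never more precise than a common-baseline model on the same data, and usually less. With equal variances and complete data the avoidable part of the planned variance is (1 − ρ)/2: 25%, 15%, 10% and 5% at ρ = 0.5, 0.7, 0.8 and 0.9. With the assumed loss, the day-30 figures are about 17%, 10%, 7% and 3%. The gain matters at moderate correlations and is minor from about 0.8 upward.

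The direction follows from the design. The size rests on assumed correlations, effect size, allocation and retention. The change should be made because it costs almost nothing and the planned enrolment leaves no allowance for dropout; keeping the planned model would not invalidate the trial.

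**What to change.** Keep the repeated-measures model and the unstructured matrix, and write in the SAP:

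> The model will have one baseline mean common to the three randomised arms and separate arm means at each later time point. It will include all randomised participants with a baseline record, not completers only. The intervention effect will be tested jointly over all post-baseline arm differences (6 df for treatment-seeking intentions, 4 df for clinical symptoms), followed by pairwise differences at each time point, including day 30, with 95% confidence intervals.

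Also state that the arm is not revealed before the baseline questionnaire, which the common mean requires, and name the estimation method with its missing-data assumption. The degrees of freedom match the time points the SAP now lists. If day 90 joins the same models they become 2 × 4 = 8 and 2 × 3 = 6.

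An alternative is to model the follow-up scores with baseline and baseline-by-time as covariates. That drops participants with no follow-up, and it must test group and group-by-time jointly. Once baseline is no longer a time level, group-by-time alone asks only whether the effect varies between follow-ups, so a constant effect would be detected only at the 5% error rate.

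The cost is a few lines of SAP text and syntax, with no new data.

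### The group × time interaction that tests the hypothesis fixes neither direction, arm nor visit, and as a gate it does not protect the unadjusted day-30 pairwise tests

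*Combined protocol and SAP*

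**What the plan says.** The Statistical Analysis Plan fits a full factorial repeated-measures model "across the four time points (baseline, post-intervention, 14- and 30-day follow-ups) for treatment-seeking intentions"; for the within-participant dependence, "we will specify an unstructured correlation matrix". The hypothesis is directional and concerns both video arms: "Group × time interaction terms will test the intervention effect hypothesis of greater treatment-seeking in the two video groups". The follow-on rule is "If between-group differences are found, post hoc tests will be used to compare each group pair". Day 30 is singled out for these comparisons, which are described as "including the overall changes from baseline assessment to 30-day follow-up". The rule does not say which model term has to be significant, and no adjustment for the three pairs is stated. "All statistical tests will be two-sided", at the 0.05 level.

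Under Assessment Instruments, "Three questionnaires will be conducted at pre- and post-intervention (day 1) and follow-up (day 14, day 30 and day 90". The first two of these surveys fall in one day-1 session, estimated at 7 to 9 minutes for the intervention arms. Study Procedures gives the video as 120 seconds long. No primary visit is named. The planned total is 1,200 (Lay Summary; Description of Subject Population).

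**The concern.** A directional statement about two arms is handed to an omnibus test that has no direction, does not require both arms, and treats the immediate survey on a par with days 14 and 30. If the interaction is significant, the SAP's wording lets the hypothesis be called supported whatever produced it. A short-lived response, or even an unfavourable one, could be reported as confirmation. The same result would also open the day-30 pairwise tests, where an error would look like a lasting effect.

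**Working it through.** **Inputs.** From the documents: 3 arms, 4 time points, N = 1,200, two-sided 0.05. Not in the documents and therefore assumed: equal allocation (1,200 / 3 = 400 per arm), SD 1, equal correlation r = 0.5 to 0.8 between visits, full retention, large-sample Wald tests, and effects δ of 0.10 to 0.20 SD.

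**The plan's own figure.** The 1,200 cannot be reproduced, because no effect size, SD or power is given with it. Working backwards, 400 per arm corresponds to δ = 0.198 for one pair at 80% power. That is context, not a check.

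**Degrees of freedom.** (3 − 1) × (4 − 1) = 6.

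**Interaction, effect at the post-video survey only, both video arms.**
- Between-arm sum of squares: 400 × (2/3)δ² = 266.7δ².
- The three changes from baseline have covariance (1 − r)(I + J), with inverse (I − J/4)/(1 − r). A change at one visit therefore contributes 0.75/(1 − r).
- Noncentrality: λ = 266.7 × 0.75 × δ²/(1 − r) = 200δ²/(1 − r).
- For δ = 0.15: λ = 4.5/(1 − r) = 9.0, 11.25, 15.0 and 22.5 at r = 0.5, 0.6, 0.7 and 0.8.

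| Post-only δ | r = 0.5 | r = 0.6 | r = 0.7 | r = 0.8 |
|---|---|---|---|---|
| 0.10 | 27% | 34% | 45% | 64% |
| 0.15 | 59% | 71% | 84% | 97% |
| 0.20 | 87% | 94% | 99% | >99% |

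Three other patterns give the same λ, and so the same percentages:
- an effect of size δ held at all three later visits, since 3 − 9/4 = 0.75;
- the same pattern with the sign reversed;
- an effect in one video arm only, since 400 × (2/3)δ² is unchanged.

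Under these assumptions the test cannot tell the hypothesised result from the others. With day-14/day-30 retention as low as 60%/50%, the range at δ = 0.15 is 52% to 97%.

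**Day-30 pairs after the interaction gate** (simulation; δ = 0.15 post-only, so every day-30 difference is truly zero; ranges over r = 0.5 to 0.8).

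| Rule | Any of 3 pairs significant | A video arm significantly above control |
|---|---|---|
| Interaction gate, unadjusted pairs | 10% to 12% | about 4% to 4.5% |
| No gate, unadjusted pairs | 12% | about 4.5% |
| Interaction gate, Bonferroni pairs | 4.0% to 4.4% | about 1.5% |
| 2-df day-30 gate, unadjusted pairs | 5% | 2% |

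**Trigger read as the group main effect.** The mean over four visits carries 0.75δ, because baseline contributes zero, and has variance (1 + 3r)/4. So λ = 266.7 × 0.5625δ² × 4/(1 + 3r) = 600δ²/(1 + 3r). For a sustained δ = 0.15 this is 5.4 at r = 0.5 and 3.97 at r = 0.8, so the trigger opens in 54% down to 41% of trials.

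**2-df test of change to day 30.** The variance of a change is 2(1 − r), so λ = 133.3δ²/(1 − r). For δ = 0.15 this is 6.0 to 15.0, giving 58% to 94% power. The 6-df interaction has 59% to 97% for the same sustained effect.

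**The case against.** **The documents set no target day.** Neither the SAP's hypothesis nor the protocol's first hypothesis says how long the effect must last, and the design deliberately surveys straight after the video. A reader might infer that success on an immediate effect would be a false success. The documents do not support that, since such an effect falls within the hypothesis as written. The protocol's stated interest in longer-term effects belongs to the day-90 amendment. This stands: day 30 is a choice for the sponsor to confirm. It does not rescue the test on direction or on which arm responded.

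**The trigger is not wrong on every reading.** The trigger sentence follows the interaction sentence, so the interaction is its natural meaning. That gate costs little: for a sustained 0.2 SD effect, some day-30 pair is found in 84% to over 99% of trials with it and 92% to over 99% without it. Baseline-to-day-30 change is among the follow-on tests, so a faded effect would be visible. Interaction terms, in the plural, could also mean signed arm-by-visit coefficients. What remains is that the term is unnamed, and that the main-effect reading would be a poor one.

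**The 10% to 12% is a multiplicity problem.** This stands. Unadjusted pairs give 12% with no gate at all, and Bonferroni cures it with the interaction gate kept. The gate does not create the error. It only fails to prevent it.

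**A 2-df test is also non-directional.** True. Direction is secured by the rule for making a claim, not by the gate.

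**Conclusion.** The concern holds in a limited form. A significant interaction does not by itself show more treatment-seeking in both video arms, or an effect that lasts. How often it would be significant for an immediate-only effect depends on a size the documents do not give: 27% to 64% of trials at 0.10 SD, 59% to 97% at 0.15 SD, and 87% to over 99% at 0.20 SD. Once opened by such an effect, the gate leaves a 10% to 12% chance of a false day-30 pair, of which about 4% to 4.5% favours a video arm over control.

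The interaction does not lack power for a sustained effect. Loss of power arises only if the trigger is taken as the group main effect. All percentages rest on 400 per arm, unit SD, equal correlations of 0.5 to 0.8 and full retention. This is a worthwhile and cheap improvement, not a fatal flaw.

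**What to change.** 1. Keep the interaction as the overall description of the trajectories.
2. Name the trigger. Either gate the day-30 pairs on a 2-df test of the three arms' change from baseline to day 30, or keep the interaction gate and adjust the three pairs. The 2-df gate needs no further adjustment at that visit: with three arms, if any two pairwise nulls are true so is the third, so the global test followed by the pairs is a closed procedure.
3. Claim the hypothesis for a video arm only if its own contrast with control is significant in the stated direction, and name the visit.
4. Report the post-intervention contrast separately as the immediate effect.

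The cost is SAP wording, with no new data or participants. There are two consequences. An effect that does not last to day 30 would be reported as an immediate effect only. The sponsor must also confirm day 30 as the target visit, because the SAP singles it out for the follow-on comparisons without calling it primary. The closed procedure covers one outcome at one visit, not other outcomes or visits.
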